Behavioral intervention with lifestyle and dietary modification usually achieves modest weight loss(7). While generally safe, most regain the weight lost within 5 years. Pharmacotherapy for obesity is considered for patients who have failed efforts at lifestyle modification and who have a BMI $\geq 30\text{Kg/M}^2$ or a BMI $\geq 27\text{Kg/M}^2$ in the presence of comorbidities such as diabetes(8). However, there have been significant concerns about the long-term safety of such medications and the currently available medications have relatively limited efficacy(9). Bariatric surgery is usually considered for patients who have a BMI $\geq 40\text{Kg/M}^2$ or a BMI $\geq 35\text{Kg/M}^2$ associated with comorbidities such as diabetes(8). Restrictive surgeries such as adjustable gastric banding (AGB) limit the capacitance of the stomach. Roux-en-Y gastric bypass (RYGB) is the most commonly performed bypass procedure and produces gastric restriction together with selective malabsorption. RYGB involves creation of a gastric pouch by separating the stomach across the fundus. Drainage of this 10-30ml pouch is achieved by a gastrojejunostomy. The distal end of the jejunum is then anastomosed ~ 150cm below the gastrojejunostomy effectively bypassing the distal stomach, duodenum and proximal jejunum. Duodenal switch (DS) is a variation of biliopancreatic diversion and involves a sleeve gastrectomy with division of the duodenum below the pylorus. The distal ileum is anastomosed to the short stump of the duodenum producing a ~ 100cm channel for nutrient absorption. The other end of the duodenum is closed and the remaining small bowel connected onto the enteral limb 75-100cm from the ileocecal valve. (See Ref (5) for illustrations & review). Observational studies suggest that bariatric surgery is the most effective intervention for weight loss producing an average weight loss of 30-35% that

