is maintained in ~ 60% of patients at 5 years(10). This has led to a dramatic increase in the number of procedures performed annually from 13,365 in 1998 to an estimated 102,794 in 2003(11). A newer procedure, sleeve gastrectomy (SG) is a restrictive operation which has increased dramatically; comprising 34% of the ~ 110,000 bariatric surgeries performed in 2013 and may become the most frequent bariatric procedure in North America(12). SG may be cheaper than RYGB in terms of operative costs and because it is not a malabsorptive procedure, the costs of follow-up, and care of morbidities arising from malabsorption, should be lower(13). **Bariatric surgery effectively produces sustained weight loss in obesity and is widely performed in the United States**

2) Comparative effectiveness of RYGB and SG. It has been suggested that remission rate is associated with the length of bypass (~85% for standard RYGB, ~93% for long-limb RYGB and ~98% with duodenal switch(14; 15). Recent prospective, randomized controlled trials have however reported lower remission rates for diabetes with RYGB, although it remains superior to medical therapy(16-18). Kashyap et al. has suggested that differences in fat loss and β -cell function between RYGB and SG occur ≥ 1 year after surgery(19). Of the 2 studies with 3 year follow-up, one undertaken in nondiabetic subjects(20) did not demonstrate clear differences in weight loss while in the other (diabetic subjects) there were small, but significant, differences with RYGB superior to SG in terms of weight and glycemic control(21). However, there are obvious anatomic differences between procedures which result in differences in enteroendocrine secretion: postprandial GLP-1 concentrations are lower after SG compared to RYGB in the comparative studies undertaken in humans(19; 22-25). On the other hand, a liquid meal, especially after gastric restriction, may not recreate conditions present after a solid meal(26). Whether these differences can explain a divergence in metabolic outcomes remains unknown.

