Study Subjects: A total of 50 subjects (25 post-RYGB and 25 post-SG) will be recruited. We will recruit otherwise healthy subjects who have undergone bariatric surgery within the past 10 years... We will exclude subjects with diabetes post-bariatric surgery. Healthy status will indicate that the participant has no known active systemic illness and no history of symptomatic microvascular or macrovascular disease. To be eligible subjects must be willing to participate in all the studies outlined. **Screening Visit:** Subjects will provide written informed consent. To ensure they are healthy, subjects will undergo a history and physical examination; blood collection for complete blood count and chemistry group; urine collection to exclude pregnancy, vital signs, blood pressure, pulse, height and weight.. Habitual activity levels (55), and bowel symptoms (56) will be assessed. **Body Composition:** % body fat will be measured using dual-energy X-ray absorptiometry (iDXA scanner; GE, Wauwatosa, WI).

Exclusion Criteria: Subjects <20 years of age will not be studied to minimize the possibility of type 1 diabetes. Subjects > 70 years of age will not be studied to minimize the potential confounding effects of age on glucose tolerance. Healthy status will indicate that the participant has no known active systemic illness.

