
1) Power Calculation: In a prior experiment we observed an overall mean value \pm (SD) of Gastric Emptying = $145 \pm (27)$ min(60) and $745 \pm (86)$ Cal(44). Assuming similar variation, 25 subjects per group would provide approximately 85% power (at a 2-sided 0.05 α level), to detect a 15% change in GE₅₀ (time taken to empty 50% of gastric contents) and a 10% change in caloric intake in each group in response to Exendin-9,39.

1) Statistical Analysis: Data will be presented as (observed) mean \pm SEM. The initial analyses will compare the within-group effect of treatment (Exendin-9,39) with the data observed in the study where saline is infused. This analysis will use a paired t-test, or signed-rank test, as warranted. An ANCOVA model incorporating the corresponding baseline study value as a covariate (e.g. GE₅₀) will be used to test differences in the response to Exendin-9,39 between groups (RYGB vs. SG). The ANCOVA model will also include age, gender and weight as covariates. A p -value < 0.05 will be considered to be statistically significant.

1) Interpretation: We will test the hypothesis that blockade of the GLP-1 receptor (GLP1R) in subjects after RYGB increases caloric intake to amounts that do not differ from those consumed after SG in the presence or absence of Exendin-9,39 infusion. We anticipate that after RYGB, subjects presented with a free choice buffet will eat less than subjects after SG during saline infusion. However, Exendin-9,39 increases caloric intake during a free choice buffet after RYGB. This supports the suggestion that the high concentrations of GLP-1 observed after RYGB alters feeding behavior, decreasing caloric intake. Given the lower concentrations of GLP-1 observed after eating in SG, we anticipate that Exendin-9,39 will have little effects, if any, on caloric intake in subjects post-SG.

To test our secondary hypothesis, we will measure gastrointestinal transit using a labelled meal as outlined above during the two studies. We anticipate that in subjects after RYGB, inhibition of endogenous GLP-1 by Exendin-9,39 will accelerate gastrointestinal implying that the high concentrations of GLP-1 observed after RYGB delay gastrointestinal transit. Conversely, in the absence of very significant elevations in endogenous GLP-1 after SG, we expect little effect of Exendin-9,39 on gastrointestinal transit – as observed previously in subjects with an intact upper gastrointestinal tract (1).

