undergo a history and physical examination to ensure that they fulfill entry criteria. If eligible, they will be asked to undergo determination of body composition. Subjects will be admitted on the morning of the study day. The morning of the study, a cannula will be placed to allow IV infusion. Infusions will be started. In addition a retrograde hand vein for blood draws will be placed. This hand will be placed in a Perspex hot-box heated to 55 deg C. Blood will be sampled several times (via the retrograde hand vein) to obtain arterialized venous samples. Subjects will be studied in random order (at least 2 weeks apart).

Population: Subjects will be recruited from Mayo Clinic Nutrition Clinic, Olmsted County residents and surrounding counties, who have previously indicated a willingness to participate in research – and who meet entry criteria. The racial composition of the county is outlined in the table below (%) using data from the 2000 population census. No children or prisoners will be recruited.

	American Indian or Alaskan Native	Asian or Pacific Islander	Black, not of Hispanic Origin	Hispanic	White, not of Hispanic Origin	Other	Total
Female	0.15	2.8	1.8	1.5	43.8	0	51.5
Male	0.15	2.8	1.8	1.5	43.7	0	48.5
Total	0.3	5.6	3.6	3.0	87.5	0	100.0

Research Materials: We will be obtaining blood samples to measure hormone and glucose concentrations.

Recruitment of Subjects: Subjects will be recruited by means of referral, advertisement, past study participants who have consented to be contacted for future research and from the Mayo Clinic Nutrition Clinic. Study participants that meet eligibility may be contacted by letter or phone call. Individuals expressing interest may be contacted by phone or e-mail, where a member of the study team will review inclusion/ exclusion criteria. Eligible subjects will be invited to participate in the study and to come to the CRTU for a screening visit.

The following are exclusion criteria;

- (a) Age < 20 or >70
- (b) For female subjects: positive pregnancy test
- (c) Functional or organic bowel symptoms
- (d) Any systemic illness, microvascular or macrovascular disease
- (e) Subjects with diabetes post-bariatric surgery
- (f) Bariatric surgery > 10 years ago

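### Subjects whose diabetes has remitted can enter either surgery group, and the RYGB-versus-SG comparison does not account for past diabetes

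*Combined protocol and SAP*

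**What the plan says.** The diabetes rule appears twice in the combined protocol and SAP, both times in terms of status after the operation. Section IV (Study Subjects) says "We will exclude subjects with diabetes post-bariatric surgery", and the list in Section V (Human Subjects) has "e) Subjects with diabetes post-bariatric surgery". Neither mentions diabetes before surgery.

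Section IV defines healthy status as "no known active systemic illness and no history of symptomatic microvascular or macrovascular disease". Section V also excludes bowel symptoms (criterion c) and systemic or vascular disease (criterion d).

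Section II.1 notes that surgery is considered at a lower BMI threshold when it is "associated with comorbidities such as diabetes(8"), so some candidates will have had diabetes before the operation. Section II.2 reports a suggestion that "remission rate is associated with the length of bypass (~85% for standard RYGB", with higher figures for longer bypasses), and then adds: "Recent prospective, randomized controlled trials have however reported lower remission rates for diabetes with RYGB". Of two studies with three-year follow-up, the one in diabetic subjects found small but significant differences, "with RYGB superior to SG in terms of weight and glycemic control".

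Only the order of the two infusion days is randomised (Section IV, Experimental Design). For the RYGB-versus-SG difference in response, Statistical Analysis specifies an ANCOVA on the corresponding baseline study value and adds: "The ANCOVA model will also include age, gender and weight as covariates".

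**The concern.** Whether a formerly diabetic person passes the diabetes exclusion depends on what happened after the operation, and the operation defines the groups being compared. If remission differs by procedure, or if diabetic patients were steered towards one procedure, the groups can differ in their share of formerly diabetic people. Nothing in recruitment or in the model addresses that.

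The primary hypothesis is a between-group statement: caloric intake after RYGB under receptor blockade matches intake after SG. The secondary hypothesis contrasts the transit response between procedures. If past diabetes changes the response to Exendin-9,39, an imbalance could produce a RYGB-SG difference that is not due to the procedure. It could equally mask a real one, which matters when the hypothesis is that intakes do not differ.

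**Working it through.** **1. Can remitted diabetes pass the criteria?** Criterion (e) tests status after surgery only. Criterion (d) might seem to cover past diabetes, but Section IV qualifies systemic illness as active and asks about history only for symptomatic vascular disease. If (d) already removed past diabetes, a separate criterion limited to post-operative diabetes would be unnecessary. Uncomplicated, remitted diabetes is therefore admissible.

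**2. Does the analysis account for it?** The paired Exendin-9,39 versus saline comparison within each surgery group uses each subject as their own control, so group composition does not confound it. In the ANCOVA, the baseline study value (taken here as the saline-day value) can absorb much of a difference in level. It does not absorb a different response to Exendin-9,39. Pre-operative diabetes is not a covariate, a balancing factor or the subject of a sensitivity analysis.

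**3. The plan's own figure.** Section IV states about 85% power with 25 per group, two-sided 0.05.
- Caloric intake: 10% of 745 = 74.5 Cal; 74.5/86 = 0.866. A two-sample t calculation gives 85.1%, which reproduces the figure.
- Gastric emptying: 15% of 145 = 21.75 min; 21.75/27 = 0.806. The same calculation gives 79.7%, or 86.2% for a 15% decrease on the log scale.

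This power statement concerns the change within each group, so the present point does not rest on it. The 74.5 Cal and 21.75 min are used below only as a yardstick.

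**4. Illustrative gap between groups.** With pre-operative prevalence p and remission r, the share of eligible people with past diabetes is p·r / (1 − p·(1 − r)). For RYGB, r = 0.85 is the Section II.2 figure, which that section says later trials did not reach. All values of p and all SG values of r are assumptions. Prevalence is set equal in the two pools.

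| p | RYGB share, r = 0.85 | SG share, r = 0.40 (gap) | SG share, r = 0.60 (gap) | SG share, r = 0.85 (gap) |
|---|---|---|---|---|
| 0.20 | 17.5% | 9.1% (8.4) | 13.0% (4.5) | 17.5% (0) |
| 0.30 | 26.7% | 14.6% (12.1) | 20.5% (6.2) | 26.7% (0) |
| 0.40 | 36.2% | 21.1% (15.1) | 28.6% (7.6) | 36.2% (0) |
| 0.50 | 45.9% | 28.6% (17.4) | 37.5% (8.4) | 45.9% (0) |

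The gap is 0 to 17 percentage points. Lower RYGB remission generally narrows it: with p = 0.30, r = 0.60 for RYGB and 0.40 for SG, the shares are 20.5% and 14.6%, a gap of about 6 points instead of 12.1.

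**5. Illustrative bias.** Bias = gap × shift in response per formerly diabetic subject. The documents give no value for that shift. Setting it to the whole detectable effect:
- Intake: 0 to 0.174 × 74.5, that is 0 to 12.9 Cal.
- Gastric emptying: 0 to 0.174 × 21.75, that is 0 to 3.8 min.

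Assume the SD of the change in intake is 86, which corresponds to a within-subject correlation of 0.5. The standard error of the between-group difference is then 86 × √(2/25) = 24.3 Cal. The chance of declaring a difference when the procedures do not differ in response rises from 5.0% to at most 8.3%.

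**6. Cost of adjusting.** On the same assumptions, power for a 74.5 Cal between-group difference is 85.0% with 44 residual degrees of freedom (50 subjects less six parameters: intercept, group and four covariates). With one more covariate it is 84.9%, or 83.1% if that covariate shares 5% of its variance with group.

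**The case against.** The strongest reply is that the documents do not show an imbalance. A reader might infer from Section II.2 that the protocol says remission differs between RYGB and SG. It does not. The remission figures there compare bypass lengths, no SG rate is given, and the RYGB advantage comes from one study, is described as small, and concerns weight and glycemic control rather than remission. A reader might also infer a large gap on the view that surgeons prefer RYGB for diabetic patients, but no document says so or gives pre-operative rates by procedure. All of this stands, so only a possible imbalance is claimed.

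Second, criteria (c) and (d) remove some people with complicated past diabetes, and the paired design with a baseline covariate means that past diabetes must change the response and not merely the level. This also stands, and it reduces the problem. It does not close the gap for uncomplicated remitted diabetes.

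Third, nothing in the documents shows that remitted diabetes alters the response to Exendin-9,39. The reference list includes work on gastric volumes in diabetes with cardio-vagal dysfunction and on diabetic gastroparesis, which makes the factor relevant to the outcomes but does not establish such an effect. The shift in step 5 is purely hypothetical.

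Fourth, chance alone matters as much at this size. At a 30% share with 25 per group, the SD of the difference in proportions is √(2 × 0.3 × 0.7/25) = 0.13, or 13 points. Chance imbalance is already reflected in the standard error, whereas a systematic one is not. Recording the variable and adjusting for it helps with both.

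**Conclusion.** The point holds as a modest, avoidable gap in the between-group analysis. People with remitted diabetes can enter either group, their proportion may differ because surgery type is not randomised, and the ANCOVA does not account for a different response in them. The within-group comparisons are sound in this respect.

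The size cannot be computed from the documents and may be zero, and the direction is unknown. The illustrated limits (17 points, 12.9 Cal, 3.8 min, 8.3% type I error) depend on the assumed prevalence, the assumed SG remission, an RYGB rate that the protocol itself tempers, and an assumed shift equal to the full detectable effect.

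A reader might go further and conclude that formerly diabetic people should be excluded or limited per group. The documents do not support that. The rule addresses current diabetes, and narrowing entry is a trade-off of recruitment and scope, not the correction of an error.

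**What to change.** Use the history already taken at the screening visit:
- Record pre-operative diabetes (yes/no) for every subject and report it by surgery group.
- Add it to the between-group ANCOVA in Section IV, Statistical Analysis, beside the covariates already listed.
- Repeat the RYGB-versus-SG comparison in never-diabetic subjects as a sensitivity analysis. A main-effect covariate assumes that past diabetes shifts the response equally in both groups; the restricted analysis does not need that assumption.

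The cost is one yes/no item, one degree of freedom and some precision if past diabetes is associated with group (step 6). The sensitivity analysis will have fewer subjects and should be read through its estimate and confidence interval, not its p-value. Eligibility need not change.
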